## 7.5 Multiplicity Adjustment

To control the Type-1 error rate at a level of 0.05, a hierarchical gate keeping procedure will be applied to test the significant difference between the treatment groups in the primary and secondary endpoints in the following order:

- 6MWD
- TTCW
- WHO Functional Class

Each test will be evaluated at the appropriate p-value as per the alpha spending function. The procedure will stop if lack of significance is found for any of the variables and the remaining test(s) in the sequence (as mentioned above) will also be concluded as non-significant.

## 7.6 Tertiary Analysis

All tertiary analysis will be performed on ITT analysis set. No multiplicity adjustments will be done for any of the tertiary endpoints analysis. Missing data will be imputed using Last Observation Carried Forward Rule (LOCF).

For all tertiary continuous endpoints if normality assumptions fail then log transformed analysis will be performed. If the normality assumptions still fails then analysis will be performed on the ranked data.

### 7.6.1 Quality of Life (SF-36 v2)

All the SF-36 continuous components will be analyzed using ANCOVA model at Week 18 with the same factors/covariates as given for secondary parameter WHO functional class (Table 28). All the tests will be one sided.

In addition, the separate proportions analysis on responders (defined as subjects having improved 6MWD post baseline) will be performed on each component. The same analysis will also be replicated for non-responders.

**Hypothesis:**

$H_0: \mu_{iNO\ 75} = \mu_{Placebo}$  versus  $H_1: \mu_{iNO\ 75} > \mu_{Placebo}$  for at least one realization.

**Direction of Difference:** Higher the Better. Higher the score better the health related quality of life (HRQoL)

	Component
1	Physical Functioning (PF)
2	Role- Physical (RP)
3	Bodily Pain (BP)
4	General Health (GH)
5	Vitality (VT)
6	Social Functioning (SF)
7	Role-Emotional (RE)
8	Mental Health (MH)

**Table 28: Summary of SF 36 Analysis**

Variable	Model	Population/ Criteria	Factors
The Change from baseline in Physical Functioning (PF)	ANCOVA at Week 18	ITT	Treatment Group, Prostanoid Usage and Baseline Score.
The Change from baseline in Role-Physical (RP)	ANCOVA at Week 18	ITT	Treatment Group, Prostanoid Usage and Baseline Score.
The Change from baseline in Bodily Pain (BP)	ANCOVA at Week 18	ITT	Treatment Group, Prostanoid Usage and Baseline Score.
The Change from baseline in General Health (GH)	ANCOVA at Week 18	ITT	Treatment Group, Prostanoid Usage and Baseline Score.
The Change from baseline in Vitality (VT)	ANCOVA at Week 18	ITT	Treatment Group, Prostanoid Usage and Baseline Score.
The Change from baseline in Social Functioning (SF)	ANCOVA at Week 18	ITT	Treatment Group, Prostanoid Usage and Baseline Score.
The Change from baseline in Role-Emotional (RE)	ANCOVA at Week 18	ITT	Treatment Group, Prostanoid Usage and Baseline Score.

Variable	Model	Population/ Criteria	Factors
The Change from baseline in Mental Health (MH)	ANCOVA at Week 18	ITT	Treatment Group, Prostanoid Usage and Baseline Score.

### 7.6.2 Change in Pulmonary Hemodynamics Measured by Right Heart Catheterization (RHC)

For study part I, the change from baseline for the following at Week 18 will be analyzed using ANCOVA at Week 18 with the same factors/covariates as given for secondary parameter WHO functional class (section 7.4.2).

1. Cardiac output [CO],
2. Cardiac index [CI],
3. Mean pulmonary artery pressure [mPAP],
4. Mean pulmonary capillary wedge pressure [mPCWP],
5. Systolic pulmonary artery pressure [sPAP],
6. Diastolic pulmonary artery pressure [dPAP],
7. Pulmonary vascular resistance [PVR],
8. PVR Index
9. Oxygen saturation by pulse oximeter [SpO2],
10. Mixed venous O2, and
11. Right atrial pressure [RAP]

**Table 29: Summary of RHC Analysis**

Variable	Model	Population	Factors
The Change from baseline in Cardiac Output at Week 18	ANCOVA	ITT	Treatment Group, Prostanoid Usage and Baseline
The Change from baseline in Cardiac index [CI] at Week 18	ANCOVA	ITT	Treatment Group, Prostanoid Usage and Baseline
The Change from baseline in Mean pulmonary artery pressure [mPAP] at Week 18	ANCOVA	ITT	Treatment Group, Prostanoid Usage and Baseline
The Change from baseline in Mean pulmonary capillary wedge pressure [mPCWP] at Week 18	ANCOVA	ITT	Treatment Group, Prostanoid Usage and Baseline

Variable	Model	Population	Factors
The Change from baseline in Systolic pulmonary artery pressure [sPAP] at Week 18	ANCOVA	ITT	Treatment Group, Prostanoid Usage and Baseline
The Change from baseline in Diastolic pulmonary artery pressure [dPAP] at Week 18	ANCOVA	ITT	Treatment Group, Prostanoid Usage and Baseline
The Change from baseline in Pulmonary vascular resistance [PVR] at Week 18	ANCOVA	ITT	Treatment Group, Prostanoid Usage and Baseline
The Change from baseline in Pulmonary vascular resistance [PVR] Index at Week 18	ANCOVA	ITT	Treatment Group, Prostanoid Usage and Baseline
The Change from baseline in Oxygen saturation by pulse oximeter [SpO2] at Week 18	ANCOVA	ITT	Treatment Group, Prostanoid Usage and Baseline
The Change from baseline in Mixed venous O2 at Week 18	ANCOVA	ITT	Treatment Group, Prostanoid Usage and Baseline
The Change from baseline in Mixed venous O2 at Week 18	ANCOVA	ITT	Treatment Group, Prostanoid Usage and Baseline
The Change from baseline in Right atrial pressure [RAP] at Week 18	ANCOVA	ITT	Treatment Group, Prostanoid Usage and Baseline

### 7.6.3 Change in Echocardiogram Measurements Right Ventricular Function and Left Ventricular Function from Baseline

Analysis will be performed by cardiac imaging core laboratory at the Brigham and Women's Hospital.

### 7.6.4 Change in NT-proBNP from Screening to 18 Weeks

The change from screening for log transformed NT-proBNP at Week 18 will be analyzed using ANCOVA model at week 18, with the same factors/covariates as given for secondary parameter WHO functional class (Table 30).

#### Hypothesis:

$H_0: \mu_{iNO\ 75} = \mu_{Placebo}$  versus  $H_1: \mu_{iNO\ 75} \neq \mu_{Placebo}$  for at least one realization.

**Table 30: Summary of NT-proBNP Analysis**

Variable	Model	Population	Factors
The Change from baseline in NT-proBNP at Week 18	ANCOVA	ITT	Treatment Group, Prostanoid Usage and Baseline

### 7.6.5 Change in Borg dyspnea Score Immediately Following 6MWT

The change from baseline for Borg Dyspnea at Week 18 will be analyzed using the ANCOVA model with same factors/covariates given for secondary parameter WHO functional class (Table 31).

#### Hypothesis:

$H_0: \mu_{iNO\ 75} = \mu_{Placebo}$  versus  $H_1: \mu_{iNO\ 75} > \mu_{Placebo}$  for at least one realization.

**Table 31 Summary of Borg Dyspnea Analysis**

Variable	Model	Population	Factors
The Change from baseline in Borg Dyspnea at Week 18	ANCOVA	ITT	Treatment Group, Prostanoid Usage and Baseline

For open label period change in Borg Dyspnea at month 4, 8 and 12 from baseline and week 18 will be analysed using ANCOVA as defined above.

### 7.6.6 Change in 6MWD as Related to Degree of Drug Adherence from Baseline to 18 Weeks

The change from baseline in 6MWD related to degree of drug adherence at Week 18 will be analyzed using the same model as given for secondary parameter WHO functional class (Table 32).

The analysis will be replicated for following categories:

- 1) Average Compliance < 8 hours per day
- 2) Average Compliance  $\geq$  8 hours per day
- 3) Average compliance <12 hours per day
- 4) Average Compliance  $\geq$  12 hours per day
- 5) Average Compliance  $\geq$  16 hours per day

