6.1.3. Tertiary Objectives

The tertiary objectives in this study are:

1. To evaluate changes in health-related quality of life using the Short Form-36 (SF-36) version 2 health survey
2. To evaluate the impact of iNO on pulmonary hemodynamics in a subset of subjects
3. To evaluate the changes in right ventricular (RV) and left ventricular (LV) function as measured by echocardiography, in a subset of subjects
4. To evaluate change in N-terminal of the prohormone brain natriuretic peptide (NT-proBNP)
5. To evaluate change in Borg dyspnea score immediately following 6-minute walk test (6MWT)
6. To evaluate change in 6MWD as related to degree of correlation between drug adherence and clinical efficacy measurement
7. To evaluate subjects with unsatisfactory clinical response
8. To evaluate the impact of iNO on frequency of heart-lung or lung transplantation, and deaths while awaiting transplantation
9. To evaluate the impact of iNO on medical resource utilization

6.2. Part 2 -Open Label Period:

6.2.1. Primary Objective:

1. To Evaluate the long term safety and tolerability of iNO

6.2.2. Secondary Objective:

1. To evaluate the change in exercise tolerance in subjects who switch from placebo to active therapy

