16. STATISTICAL CONSIDERATIONS

This section provides a general description of the statistical methods to be used in analyzing both safety and efficacy data. The key statistical issues or considerations will be addressed. A more detailed statistical analysis plan will be provided in a separate document that will be finalized before unblinding of treatment assignment.

Unless otherwise specified, all statistical tests will be one-sided with a significance level of 0.025. Summary statistics will be provided for all study variables with descriptive statistics (number of observations, mean, standard deviation, median, minimum, and maximum) for numerical (or continuous) variables and with frequency and percentage for categorical variables.

All statistical analysis will be conducted using SAS version 9.2 or higher (SAS Institute Inc., Cary, NC).

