16.2. Sample Size Determination

Interim Analysis will be conducted by an independent DMC after 18-week 6MWD data are available from 75 patients. The purpose of the interim analysis is to stop the trial for an early efficacy or futility conclusion or to continue the trial to 150 or 188 - patients (total randomized is higher to account for an anticipated 20% dropout rate). Group sequential early stopping criteria and sample size re-estimation methodology are further described in the statistics section of this protocol. They are constructed to control overall type 1 error at 0.025, 1-sided. Simulations assuming true underlying mean treatment difference in 6MWD ranging from 30-70 meters and standard deviations from 50 to 75 meters yielded >87% power for all cases except the most extreme case (mean difference 30 meters and SD 75), for which power was ~71%.

Subjects who do not comply with the required device adherence, as well as who do not meet the study entry criteria at Week 2, will be withdrawn from the study.

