## 5.4 Sample Size

The sample size calculation for this study was performed assuming one interim analysis. The purpose of the interim analysis is to stop the trial for efficacy or futility conclusion or to continue the trial to 150 or 188 patients.

The sample size calculations were performed using following two designs:

- 1) Design1: Group sequential early stopping criteria and
- 2) Design 2: Sample size re-estimation methodology

Design 1: Traditional group sequential design (GSD) alpha spending function  $\Gamma=3$  ([Hwang, Shih, deCani, 1990](#)) is used to control the overall type 1 error at 0.025, 1-sided.

Design 2: This is the "promising zone" sample size re-estimation (SSR) design of [Mehta & Pocock \(2011\)](#), which uses the [Cui, Hung, Wang \(1999\)](#) method of analysis to combine the test statistics for the separate analyses of the IA and post-IA parts of the trial, if the trial does not stop at IA.

The final analysis is via weighted Z statistic using equal weights for the IA and post IA test statistics. It requires  $p < 0.0229$  1-sided for statistical significance to control the overall type 1 error level at 0.025 1-sided with  $\Gamma=3$  error spending function ([Hwang, Shih, deCani 1990](#)).

A sample size of 150 patients (75 in each group) with simulations assuming true underlying mean treatment difference in 6MWD ranging from 30-70 meters and standard deviation from 50-70 meters yielded  $> 87\%$  power for both designs (for all cases except the most extreme case (mean difference of 30 meters and S.D 75, power for this combination was 71%).

The estimated conditional power (CP) and predictive power (PP) based on interim estimated SD and mean differences observed on 75 subjects with a planned final sample size of 150 is shown in ([Table 22](#)).

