**Table 22: Conditional and Predictive Power**

S.D	Mean Difference	Interim Z Statistics	Conditional Power (CP)	Predictive Power (PP) with vague prior#	Predictive Power (PP) with informative prior*
50	30	2.598	0.991	0.951	0.994
	40	3.464	$>0.999$	0.998	$>0.999$
	50	4.33	$>0.999$	$>0.999$	$>0.999$
	60	5.196	$>0.999$	$>0.999$	$>0.999$
	70	6.062	$>0.999$	$>0.999$	$>0.999$
60	30	2.165	0.934	0.853	0.974
	40	2.887	0.998	0.981	0.998
	50	3.608	$>0.999$	0.999	$>0.999$
	60	4.33	$>0.999$	$>0.999$	$>0.999$

S.D	Mean Difference	Interim Z Statistics	Conditional Power (CP)	Predictive Power (PP) with vague prior#	Predictive Power (PP) with informative prior*
	70	5.052	>0.999	>0.999	>0.999
75	30	1.732	0.739	0.669	0.912
	40	2.309	0.964	0.895	0.983
	50	2.887	0.998	0.981	0.998
	60	3.464	>0.999	0.998	>0.999
	70	4.041	>0.999	>0.999	>0.999

\*: The informative prior distribution on the treatment effect is based on estimates from a prior PAH study, in which analysis of change from baseline in 6 minute walk distance for 20 patients (7 controls, 13 treated) receiving oxygen for at least 12 hours a day yields an estimated treatment difference of 69.6 and pooled standard deviation estimate of 38.7.

#: Vague prior distribution which assumes no difference between groups.

All the sample size calculations were performed using EAST 6.4.

Using the above estimates yielded a planned sample size of 75 evaluable subjects per treatment arm (in total 150 subjects).

Further, in case the planned final analysis at N=150 (2 groups combined) is found not to have sufficient power, sample size increase could be made at IA up to a maximum of N=188 total patients (2 groups combined).

Assuming a 20% drop out rate, a total of 188 subjects (94 per treatment arm) are planned to support 150 at final analysis, with the ability to go up to 226 subjects (113 per treatment arm) to support 188 at final analysis, based on the sample size reassessment at the interim analysis.

As subjects must achieve a satisfactory adherence to the INOpulse delivery device, a dynamic randomization system will be used to ensure that approximately 94 (or 113) subjects per treatment cohort comply with the adherence criteria at Week 2. Enough subjects will be recruited such that a minimum sample size of 150 (or 188) subjects will complete 18 weeks of treatment on the INOpulse delivery device.

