### **6.2 Product Compliance (Device Adherence)**

Subjects will be supplied with products at randomization visit. The product adherence data is not captured on CRF and will be supplied via the IRT by Y Prime.

The following fields are agreed.

- Patient number
- Report Start Date
- Report End Date
- Day of Usage
- Number of Minutes of Use
- Average Usage for Period

The subject will be deemed compliant if their average daily usage is more than 12 hours.

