**Table 32: Summary of 6MWD and Drug Adherence Analysis**

Variable	Model	Population	Factors
----------	-------	------------	---------

Variable	Model	Population	Factors
The Change from baseline in 6MWD for drug adherence at Week 18	ANCOVA	ITT	Treatment Group, Prostanoid Usage and Baseline

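### SAP 7.6.6 compares iNO with placebo inside five partly nested usage categories and never estimates how the 6MWD effect changes with adherence, which is the stated objective

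*SAP*

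**What the plan says.** Protocol Section 6.1.3, item 6 (repeated in SAP Section 3.1.3) sets the objective: "To evaluate change in 6MWD as related to degree of correlation between drug adherence and clinical efficacy measurement".

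SAP Section 7.6.6 addresses it with the ANCOVA used for WHO functional class, fitted to Week 18 6MWD change. Then: "The analysis will be replicated for following categories". The five categories are average use below 8, at least 8, below 12, at least 12 and at least 16 hours per day. The only hypothesis is that the iNO mean equals the placebo mean, against iNO greater. Table 32 has a single row, "The Change from baseline in 6MWD for drug adherence at Week 18", whose factors are treatment, prostanoid use and baseline.

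On error rates, Protocol Section 16 states "Unless otherwise specified, all statistical tests will be one-sided with a significance level of 0.025", and SAP Section 7.6 makes no multiplicity adjustment for tertiary endpoints. Daily usage is supplied through the IRT; the agreed fields in SAP Section 6.2 include "Number of Minutes of Use".

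Nothing elsewhere fills the gap. Protocol Section 16.3.3 applies the primary model to continuous tertiary endpoints, Section 16.3.1 adds subgroup analyses by usage without naming an interaction, and the mITT set in SAP Section 7.1.4 only selects subjects by usage.

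**The concern.** The objective asks whether response varies with adherence. Each planned test asks whether iNO differs from placebo among subjects in one usage band. Rejecting that null shows a treatment difference in the band and says nothing about whether the difference depends on hours of use. The categories also differ greatly in size, so significance in one and not in another can arise from power alone.

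This matters because of how the trial was motivated. Protocol Section 5.1 describes a post hoc, unplanned Phase 2 finding in 35 LTOT users averaging at least 12 hours per day. SAP Section 7.6.6 is the pre-specified place to examine whether usage drives benefit, yet it repeats the same kind of within-subset comparison. A pattern of significance at or above 12 hours and none below would look like support for the rationale even if usage had no influence.

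**Working it through.** **1. Structure, without simulation.** Below 8 and at least 8 are a complementary pair, as are below 12 and at least 12. Below 8 lies inside below 12; at least 16 lies inside at least 12, which lies inside at least 8. Each subject therefore appears in two or three categories. Table 32 has no adherence term and no treatment-by-adherence term.

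**2. Inputs and the plan's own figures.** From the documents: one-sided 0.025; 150 evaluable subjects, up to 188 after re-estimation (SAP Section 5.4); differences of 30 to 70 m and SDs of 50 to 75 m (Protocol Section 16.2: "Simulations assuming true underlying mean treatment difference in 6MWD ranging from 30-70 meters"). Section 7.6.6 states no power figure, so I checked the primary design. The gamma = -3 boundaries come out at 0.00456 and 0.02288, against the stated 0.0046 and 0.0229. For 30 m and SD 75 m the interim Z is 30 / (75 × √(2/37.5)) = 1.732, as in SAP Table 22. Power is 71.4% with increase to 188 across the Protocol's promising zone and no binding futility, against about 71% stated.

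**3. Constant effect unrelated to usage, by hand.** Take N = 188, SD 60 m and effect 30 m. Assume usage is normal with mean 15 and SD 4 hours.
- Share below 12 h: Φ((12 − 15)/4) = Φ(−0.75) = 0.227, so about 42.7 subjects (21.3 per arm), leaving 145.3 (72.7 per arm) at or above 12 h.
- At least 12 h: SE = 60 × √(2/72.7) = 9.95 m; power = Φ(30/9.95 − 1.96) = 85%.
- Below 12 h: SE = 60 × √(2/21.3) = 18.4 m; power = Φ(30/18.4 − 1.96) = 37%.

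The same 30 m effect therefore has 85% power in one category and 37% in its complement.

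**4. Same scenario, simulated** (3,000 trials, ANCOVA in each category):

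| Result | Rate |
|---|---|
| At least 8 h significant | 92% |
| At least 12 h significant | 84% |
| At least 16 h significant | 55% |
| Below 12 h significant | 32% |
| Below 8 h significant | 4% |
| At least one category significant | 95% |
| At least 12 h significant and below 12 h not | about 57% |
| Treatment-by-hours interaction, one ITT model | 2.5% |

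The 57% agrees with 0.84 × (1 − 0.32) = 0.57, since the two categories share no subjects.

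**5. Sensitivity to the assumed usage** (N = 150, 8,000 trials per scenario). I used mean/SD of 17/4, 15/4 and 13/5 hours, which put 11%, 23% and 42% of subjects below 12 h. The same pattern appears in 29–56% of trials at 30 m/SD 75, 33–72% at 30 m/SD 60 and 10–73% at 50 m/SD 60. The interaction test stays at 2.1–2.8%. At least one category is significant in 74–75%, 89% and over 99.9% respectively, close to the overall treatment test (67–68%, 85–86%, 99.9%).

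**6. Selective adherence, no drug effect.** Let usage correlate 0.3 with outcome in the iNO arm only (N = 188, SD 60 m). This is a slope of 0.3 × 60/4 = 4.5 m per hour in that arm. The at-least-16 h category is significant in about 23% of trials and the on-treatment interaction in about 53%. By hand, the SE of the slope difference is (60/4) × √(2/94) = 2.19 m per hour, giving Φ(4.5/2.19 − 1.96) = 54%.

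**The case against.** Four points on the other side have weight.

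- **Endpoint wording.** Protocol Section 7.1.3, item 6 describes 6MWD change related to degree of adherence with iNO compared to placebo. A treatment comparison by usage level is a fair reading, and neither objective nor endpoint names an interaction. This stands as a reason to keep the categories. It does not supply the missing estimate of how the comparison changes across them.
- **The complementary pairs are informative.** If the effect falls by 4 m per hour around a 30 m mean, the average differences are about 51 m below 12 h and 24 m at or above it, so the reversed gradient would be visible. This stands descriptively, but the plan specifies no comparison and no measure of uncertainty for it.
- **An interaction on on-treatment hours can mislead more.** Step 6 shows 53% against 23%. This stands in full: average usage is post-randomisation behaviour, and the interaction cannot serve as a confirmatory test.
- **Low stakes.** The analysis is tertiary, outside the gatekeeping sequence and free of any multiplicity claim. That is correct and limits the severity.

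A reader might infer that the plan finds a result whenever iNO works. It does so usually, not always: about 74% of trials at 30 m/SD 75 give at least one significant category, and the low-usage categories are often non-significant. A reader might also infer that the run-in rule leaves the below-8 h category almost empty. That rule covers Weeks 0 to 2 only, and the documents give no later usage distribution for this trial. In Phase 2, 71% of LTOT users were adherent (Protocol Section 5.1), so 29% fell short of 12 hours. Finally, no passage says that significance in one category and not another will be read as proof of an adherence effect; the risk is that the planned output invites that reading.

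**Conclusion.** The concern holds as a mismatch between objective and analysis. SAP Section 7.6.6 and Table 32 do not estimate the relation between adherence and 6MWD response, and no other section does. This follows from the text and needs no distributional assumption.

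The size of the misleading pattern does need one. About 57% applies to N = 188, SD 60 m, a constant 30 m effect and usage of mean 15, SD 4 hours; across the other cases run it ranges from 10% to 73%. The explanation by subset size applies when the effect is constant. It does not mean that every observed difference between categories would be an artefact. The primary and secondary conclusions are not affected, and the change is advisable rather than essential.

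**What to change.** In SAP Section 7.6.6 and Table 32:

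1. Add one ITT model of Week 18 6MWD change with treatment, prostanoid use, baseline 6MWD, average daily hours (continuous) and treatment-by-hours. Report the slope difference in metres per hour with its 95% CI, as an estimate and not a confirmatory test.
2. Define the period over which average hours are computed, which Section 7.6.6 leaves open.
3. Present the five categories as means and CIs by arm, without significance tests within categories.
4. Label the on-treatment-hours result as non-randomised, since selective adherence alone can produce an interaction.
5. Repeat the model with run-in hours (Weeks 0 to 2) as a sensitivity analysis. State that these hours are truncated near 12 by the eligibility rule and are also recorded after randomisation, with the iNO arm at the low run-in setting.

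The cost is SAP wording and two model fits on usage data already supplied. The drawback is modest power: about 40% for a slope difference of 4 m per hour with on-treatment hours at N = 188. With run-in hours it falls to 26% if they equal on-treatment hours and 16% if the two correlate 0.7. A linear slope is also weak against a threshold: if the effect were 40 m at or above 12 h and zero below (SD 60 m, N = 150), the continuous interaction would have 22–34% power. These figures are the reason to report an interval and not a test.
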